# **10.4** Follow-up for Adverse Events

Follow all AEs and SAEs that are encountered during the protocol-specified AE reporting period (1) to resolution, (2) until the investigator assesses the subject as stable and the event is following a clinically expected outcome, or (3) until the subject is lost to follow-up or withdraws consent.

#### 11.0 STATISTICS

Statistical analyses will be performed by Astex Pharmaceuticals or its designee.

Data summaries and listings will be generated using SAS version 9.4 or a more recent version (SAS Institute Inc., Cary, NC, USA).

The statistical analysis plan and/or the clinical study report will provide additional details of the analysis, which may include details of missing and, if applicable, unused data, as well as additional sensitivity analyses of the primary and secondary variables. The clinical study report will describe deviations from the statistical analysis plan, if any.

# 11.1 Sample Size

A preliminary analysis of 5-day AUC in study ASTX727-01 shows an estimate of intra-subject CV of 0.5. A conservative CV value of 0.55 was chosen to calculate the sample size.

A total of 118 subjects in the Primary Endpoint PK Analysis Set (Section 11.2.2) included in the 2 one-sided equivalence tests for the geometric mean ratio of ASTX727 5-day AUC relative to IV decitabine 5-day AUC will provide 90% power at the statistical significance level of 0.05, when the true ratio of geometric means is 1.0, the CV under an unlogged scale is 0.55, and the 90% CI equivalence limits for the ratio of geometric means are 0.8 and 1.25. Assuming 10% of subjects may not be evaluable in the study, approximately 132 subjects will need to be randomized.

# 11.2 Analysis Sets to be Analyzed

# 11.2.1 All Subject Analysis Set

The **All Subject Analysis Set** will include information from all screened subjects, including those who did not meet the study entry criteria or who did not receive a study treatment. This data set will be used only for disposition in which all screened subjects are accounted.

# 11.2.2 Pharmacokinetics Analysis Sets

Two PK analysis sets will be used for analysis of PK data, as described below.

The **Primary Endpoint PK Analysis Set** will be used for calculating decitabine 5-day AUC0-t and bioequivalence statistical analysis. This analysis set will include decitabine daily AUC0-t from subjects who are successfully dosed in Cycles 1 and 2 (see below) and who meet the following criteria for both ASTX727 and IV decitabine dosing.

ASTX727 successful dosing: received full dose of ASTX727 within 3 hours of the intended dosing time, and no vomiting within 6 hours of dosing.

• Subjects in this analysis set will have at least 2 days of evaluable decitabine AUC0-t measurements in the ASTX727 cycle, ie, Day 1 and either Day 2 or Day 5:

- o For Day 1 to be included, subjects must have been successfully dosed on Day 1.
- o For Day 2 to be included: subjects must have been successfully dosed on Day 1 and Day 2.
- o For Day 5 to be included: subjects must have been successfully dosed on Day 4 and Day 5.

IV decitabine successful dosing: received the full dose as a 1-hour infusion.

• Subjects in this analysis set will have at least 1 evaluable day of decitabine AUC0-t measurement in the IV decitabine cycle, either Day 1 or Day 5.

The **Overall PK Analysis Set** will be used for calculating PK parameters, including decitabine daily AUC0-t, which will be used to derive the primary PK endpoint of decitabine cumulative 5-day AUC0-t exposures, and other secondary PK parameters for decitabine, cedazuridine, and cedazuridine-epimer. This analysis set will include subjects who may or may not be included in the Primary PK Analysis set and who meet the following criteria:

- Received any amount of study treatment.
- Complied with the protocol sufficiently to ensure PK samples were collected as intended.
- Provided sufficient samples to measure available plasma concentrations for decitabine, cedazuridine, and cedazuridine-epimer.

# 11.2.3 Efficacy Analysis Set

The Efficacy Analysis Set will include data from all subjects who received at least one full dose (day) of study treatment. All data will be included, and no subjects excluded because of protocol violations. Subjects will be included in the treatment group according to their randomly assigned treatment.

# 11.2.4 Safety Analysis Set

The Safety Analysis Set will include all subjects who received any amount of study treatment. All data will be included, and no subjects will be excluded because of protocol violations.

## 11.2.5 Pharmacodynamics Analysis Set

Subjects will be included in the PD Analysis Set if they have received at least one dose of study treatment and have %LINE-1 methylation data at baseline (Day 1) of Cycle 1 or 2 and on either Day 8 or Day 15 of the respective cycle.

## 11.3 Schedule of Analyses

Pharmacokinetics for the primary study endpoint, PD, and safety analyses will be performed after all evaluable subjects have completed Cycles 1 and 2. Additional secondary endpoint analyses will be performed after all subjects discontinue treatment or complete at least 6 cycles of treatment.

# 11.4 Subject Disposition

The number and percentage (n, %) of subjects enrolled, treated, lost to follow up, and withdrawn (with reason) will be summarized. Sample size for the Efficacy Analysis Set, Safety Analysis Set, PK Analysis Set, and PD Analysis Set will be clearly identified for each treatment sequence. All subjects in the All Subject Analysis Set will be included in the disposition analysis.

## 11.5 Analysis of Demographic and Baseline Data

Subject demographic and baseline characteristics will be summarized by mean, standard deviation (SD), median, minimum, and maximum for continuous variables; and by counts and percentages for categorical variables. Summaries will be provided separately for each treatment sequence and both sequences combined. The Efficacy Analysis Set will be used for the summaries.

# 11.6 Pharmacokinetics Analyses

A detailed description of the PK analyses is in the Pharmacokinetic Analysis Plan. A brief description follows below.

## 11.6.1 Primary Pharmacokinetics Endpoint Analyses

The primary PK endpoint analyses will be performed in the order presented below.

Calculation of daily decitabine AUC0-t

The Overall PK Analysis Set will be used for calculation of decitabine AUC0-t. Decitabine AUC0-t by Cycle and Day will be calculated by the linear up/log down non-compartmental method using the measured concentration-time values above the quantitation limit using Phoenix® WinNonlin.

In the case of a missed sample collection, enough data should be available for reliable calculation of the parameter AUC0-t. To be considered reliable for calculation of AUC0-t without imputation of missing data, a plasma PK profile should contain more than 5 consecutive data points with a quantifiable concentration value, including at least 3 data points beyond the Tmax, and %AUCextrap ((1-[AUC0-t/AUC0-inf])×100) should not exceed 20% for each individual profile.

Individual values of decitabine daily AUC0-t will be used for generating the Primary Endpoint PK Analysis Set from evaluable subjects as described above. A listing of individual values of decitabine daily AUC0-t Cycle and Day, and non-model-based descriptive statistics will be provided. However, decitabine daily AUC0-t from subjects who are not evaluable to be included in the Primary Endpoint PK Analysis Set will be identified in the listing but will not be included in descriptive statistics; the reason for exclusion will be provided.

Calculation of decitabine 5-day AUC0-t

The Primary Endpoint PK Analysis Set will be used to calculate decitabine 5-day cumulative AUC0-t exposures after ASTX727 treatment. The following assumptions will be used:

- Steady state is reached on Day 2 of dosing with ASTX727.
- Based on steady state achievement on Day 2, decitabine AUC0-t from Day 2 and Day 5 would be representative of daily AUC0-t on Days 2 through Day 5 in a putative 5-day dosing with ASTX727.

Therefore, to calculate total 5-day oral decitabine  $AUC_{0-t}$  exposures using PK data from 3 days sequential PK sampling, Day 1  $AUC_{0-t}$  (first ASTX727 dose) will be added to (Day 2  $AUC_{0-t}$  + Day 5  $AUC_{0-t}$ ) × 2. If  $AUC_{0-t}$  on Day 2 is not available, it will be replaced by  $AUC_{0-t}$  on Day 5; the converse is also true.

To calculate decitabine 5-day  $AUC_{0-t}$  exposures after IV decitabine, (Day 1  $AUC_{0-t}$  + Day 5  $AUC_{0-t}$ ) / 2 will be multiplied by 5, based on Dacogen prescribing information (current Dacogen Prescribing Information) that there was no accumulation on Day 5 vs Day 1 for a 5-day infusion. If  $AUC_{0-t}$  on Day 1 is not available, it will be replaced by  $AUC_{0-t}$  on Day 5; the converse is also true.

Bioequivalence statistical analysis of decitabine 5-day AUC0-t between ASTX727 and IV decitabine treatments

Decitabine AUC0-t equivalence analysis will be performed on the Primary Endpoint PK Analysis Set.

The primary endpoint, decitabine 5-day AUC0-t, will be analyzed in the log scale using a mixed effect model including fixed effects of sequence, period, and treatment, and a random effect of subject within sequence (EMA 2010; EMA 2015). The factors to be included in the model will be based on the actual treatment sequence. A 90% CI for the geometric mean ratio of 5-day AUC0-t will be obtained by applying the exponential function on the 2-sided 90% CI for the difference of mean 5-day AUC0-t between ASTX727 and IV decitabine in the log scale from the mixed effect model. The decitabine AUC0-t equivalence will be established if the 90% CI for the geometric mean ratio is contained within the interval (0.8, 1.25).

## 11.6.2 Other Pharmacokinetics Variables

Calculation of other secondary PK parameters will be performed on the Overall PK Analysis Set. Pharmacokinetics parameters will be calculated by noncompartmental analysis methods from the concentration-time data using Phoenix® WinNonlin®.

Decitabine PK parameters AUC0-inf, Cmax, Tmax, clearance (CL/F), apparent volume of distribution (Vd/F), and apparent half life (t1/2) are of secondary interest and will be reported together with AUC0-t where applicable. The PK parameters of cedazuridine and cedazuridine-epimer will be also reported.

Individual values will be listed for each PK parameter by treatment and analyte, and the following (non-model-based) descriptive statistics will be provided: number of subjects with non-missing

data, arithmetic mean, standard deviation, arithmetic percent, median, minimum, maximum, geometric mean, and geometric percent CV. Note that CL/F and Vd/F will be calculated only for decitabine and cedazuridine and will not be calculated for cedazuridine-epimer.

A population PK analysis for evaluation of various covariates and exposure-response will also be performed.

# 11.7 Efficacy Analyses

Unless otherwise specified, the Efficacy Analysis Set will be used for all efficacy analyses. Efficacy endpoints will be analyzed as one treatment group regardless of randomization.

## 11.7.1 Clinical Response

Complete response, mCR, PR, and HI (also HI-E, HI-P, and HI-N separately) will be summarized for all subjects in the Efficacy Analysis Set. The rate of each response status and its 95% Wald CIs will be provided, respectively.

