#### Efficacy

Efficacy endpoints will be analyzed for subjects in the Efficacy Analysis Set, defined as the set of all subjects who received at least one full dose (day) of study treatment. Proportions of clinical responses will be calculated for subjects in the Efficacy Analysis Set, while TI rates will be calculated based on subjects who are transfusion dependent at baseline. The 95% Wald CIs will be provided for clinical response rates and TI rates. Leukemia-free survival and OS will be presented using Kaplan-Meier estimates along with 95% CIs for medians.

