# 11.7.2 Transfusion Independence

Transfusion independence (TI) will be analyzed separately for platelet and RBC TI, the latter defined as no RBC transfusion for 56 consecutive days while maintaining hemoglobin  $\geq 8$  g/dL. Platelet TI is defined as no platelet transfusion for 8 consecutive weeks, while maintaining platelets  $\geq 20 \times 10^9$ /L. Transfusion independence rates will be calculated based on subjects who are in the Efficacy Analysis Set and who were transfusion dependent at baseline. The 95% Wald CIs will be provided separately for the RBC and platelet TI rates.

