## 1.0 INTRODUCTION

Study ASTX727-02 originally included only myelodysplastic syndromes (MDS) and chronic myelomonocytic leukemia (CMML) subjects. The Amendment 1.3 Europe (10 December 2018) expanded the subject population to include ~70 acute myeloid leukemia (AML) evaluable subjects in Europe to obtain pharmacokinetic data in the AML population to allow the PK-bridging approach for marketing approval in the EU. This Statistical Analysis Plan (SAP), which is based on the ASTX727-02 protocol amendment 2.6 Europe (dated 27 January 2021), will only describe analysis of AML subjects included in the ASTX727-02 study (ASTX727-02 SAP [AML]). There is a separate SAP which has been approved earlier for analysis of only MDS/CMML subjects included in the ASTX727-02 study (ASTX727-02 SAP). The ASTX727-02 SAP (AML) details the methodology to be used in analyzing the AML subject data and outlines the specifications for data to be included in the Tables, Listings and Figures (TLFs) of the Clinical Study Report for AML subjects. The analyses specified in this document supersede the high-level analysis plan described in the protocol. Analyses and statistical reporting for ASTX727-02 AML subjects, with the exception of the analyses that are described in a separate Pharmacometric Analysis Plan (PAP) and a separate Cardiac Clinical Statistical Plan (CCSP) for AML subjects, will be conducted by Astex Pharmaceuticals Biostatistics department using SAS version 9.4 or higher. Pharmacokinetics (PK) analyses of plasma decitabine, cedazuridine, and cedazuridine-epimer are described in the PAP and will be conducted by pharmacokinetic specialists and statisticians at Certara Strategic Consulting. Analyses of ECG data and exposure vs. QTc Interval assessment are described in the CCSP and will be conducted by expert cardiologists and statisticians at eResearch Technologies, Inc. (ERT).

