**Table 2: Modified IWG 2003 AML Response Criteria**

Response a	ASTX727-02 Specific Criteria
CR	ANC $\geq$ 1000/ $\mu$ L, Platelets $\geq$ 100,000/ $\mu$ L, independence from RBC and platelet transfusions over the past week, no leukemic blasts b <5% leukemic blasts
CRi	All CR criteria except ANC <1000/ $\mu$ L or Platelets <100,000/ $\mu$ L
CRp	All CR criteria except Platelets <100,000/ $\mu$ L and platelet transfusions over the past week
PR	All CR criteria except decrease of $\geq$ 50% in leukemic blasts to level of 5% to 25%

ANC=absolute neutrophil count; CR=complete response; CRp=complete response with incomplete platelet recovery; CRi=CR with incomplete blood count recovery; PR=partial response.

a Responses are based on both PB and BM conditions.

b For the purpose of response assessment and according to published IWG criteria, blasts may be seen in PB as rare PB blasts may be identified during regeneration, but the subject is in CR if BM blasts are <5% with no Auer rods.

Source: [Cheson et al 2003](#); [Kantarjian et al 2012](#)

For subjects who experience different response levels at different visits, the best response (see [Table 2](#)) will be used for summary and analyses. Overall objective response will be the number of subjects achieving CR, CRi, and PR with each subject counted once according to their best response. CRp, a subcategory of CRi will be listed under CRi. Composite response rates, CR + CRi (either CR or CRi), CR + CRi + PR (either CR or CRi or PR), CR + CRh (either CR or CRh) and CRh, will also be included in the response analysis.

Subjects with these different response categories will be listed and summarized using frequency counts and proportion of subjects with each category. The 95% Clopper-Pearson confidence interval will be provided for each response rate. Subgroup analyses such as by age category ( $<75$ ,  $\geq 75$ ) may be performed.

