### 7.5.4 Transfusion Independence

Transfusion independence (TI) will be analyzed separately and simultaneously for platelet and RBC transfusions. Transfusion dependence (TD) and transfusion independence are defined as follows:

- Transfusion dependence at baseline: documentation of 2 units or more of transfusion within 56 days of the first dose of study treatment.
- Post-treatment transfusion independence: no transfusion for 56 consecutive days or more after the first dose of study treatment while maintaining hemoglobin  $\geq 8$  g/dL (RBC TI) or maintaining platelets  $\geq 20 \times 10^9/L$  (platelet TI).

Post-treatment transfusion independence rate will be calculated separately and simultaneously for RBC transfusion independence and platelet transfusion independence as the number of subjects who are transfusion independent post treatment (n) among those who were transfusion dependent at baseline (N). The 95% Clopper-Pearson CI for transfusion independence rates will be provided. The same analyses will be performed for 84-day and 112-day transfusion independence, defined as no transfusion for 84 consecutive and 112 consecutive days, respectively, while maintaining hemoglobin  $\geq 8$  g/dL (RBC TI) or maintaining platelets  $\geq 20 \times 10^9/L$  (platelet TI).

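### The protocol's Wald 95% intervals for MDS/CMML response and transfusion-independence rates have no fallback and fail if counts are small

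*Protocol*

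**What the plan says.** Protocol 11.7.1 covers CR, mCR, PR and HI, with HI-E, HI-P and HI-N also shown separately: "The rate of each response status and its 95% Wald CIs will be provided, respectively". Protocol 11.7.2 states: "The 95% Wald CIs will be provided separately for the RBC and platelet TI rates". The Synopsis (Efficacy) repeats the method for both families: "The 95% Wald CIs will be provided for clinical response rates and TI rates". None of the three places gives an alternative for sparse counts.

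Two denominators apply. Response rates use the Efficacy Analysis Set, pooled over sequences: "Efficacy endpoints will be analyzed as one treatment group regardless of randomization". TI rates use a subset: "Transfusion independence rates will be calculated based on subjects who are in the Efficacy Analysis Set and who were transfusion dependent at baseline". The protocol gives no expected response rates and no expected number of transfusion-dependent subjects.

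The SAP supplied covers AML subjects only. For them, 7.5.1 says "The 95% Clopper-Pearson confidence interval will be provided for each response rate" and 7.5.4 says "The 95% Clopper-Pearson CI for transfusion independence rates will be provided". For the MDS/CMML subjects, SAP 1.0 points elsewhere: "There is a separate SAP which has been approved earlier for analysis of only MDS/CMML subjects included in the ASTX727-02 study". That document was not available for this review.

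**The concern.** The Wald interval takes its standard error from the observed proportion, so at 0 or n events the standard error is zero and the interval collapses to a point. With a handful of events it is too short, and its lower limit falls below zero.

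Sparse cells are plausible here, though not demonstrated. Under Protocol Table 8, a PR needs marrow blasts still above 5% after a fall of at least 50%. Only subjects with more than 10% blasts at baseline can therefore qualify, yet the denominator is the whole Efficacy Analysis Set. The RBC and platelet TI rates each use only subjects dependent on that product at baseline, and nothing in the design fixes the size of those subsets.

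At stake is how precision is reported. These intervals are the only stated measure of uncertainty for response and TI rates. In sparse cells they would overstate precision, and a zero count would get no upper bound.

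**Working it through.** **Inputs.** From the documents: the Wald method, pooling over sequences, and a denominator of at most about 132 (Protocol 5.1 and 11.1). Assumed, because the documents give no value: true rates of 1% to 50%, TI subsets of 20, 40 and 60, and every randomized subject dosed.

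**The plan's own figure.** The protocol gives no precision figure for these rates. Its only sizing figure is 118 evaluable and 132 randomized. Two one-sided tests with CV 0.55, true ratio 1.0 and limits 0.8 to 1.25 give power of 90.5% at N = 118 and 89.9% at N = 116. Then 118 / 0.90 = 131.1, rounded up to 132. Both figures reproduce, so 132 is used as the upper bound for the response denominator.

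**Formulas.**
- Wald: p̂ ± 1.96 √(p̂(1 − p̂)/n), with p̂ = x/n.
- Clopper-Pearson upper limit at x = 0: 1 − 0.025^(1/n).
- Exact coverage at true rate p: the sum of Binomial(n, p) probabilities over every x whose interval contains p.

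**Individual intervals.**

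| Result | Wald | Clopper-Pearson |
|---|---|---|
| 0/132 | 0 to 0 | 0 to 2.8% |
| 1/132 | −0.7% to 2.2% | 0.0% to 4.1% |
| 3/132 | −0.3% to 4.8% | 0.5% to 6.5% |
| 0/20 | 0 to 0 | 0 to 16.8% |
| 26/132 | 12.9% to 26.5% | 13.3% to 27.5% |
| 12/40 | 15.8% to 44.2% | 16.6% to 46.5% |

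For example, 1/132 gives p̂ = 0.00758 and standard error √(0.00758 × 0.99242 / 132) = 0.00755, so the limits are 0.00758 ± 0.0148. The lower limit is negative for 1 to 3 events at n = 20, 30, 40, 60, 118 and 132.

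**Wald coverage at n = 132.**

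| True rate | 1% | 2% | 3% | 5% | 10% | 20% | 30% |
|---|---|---|---|---|---|---|---|
| Coverage | 73.4% | 92.9% | 90.2% | 89.4% | 94.7% | 94.5% | 94.0% |

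At a true rate of 1%, only x = 1 to 6 give an interval containing 1%. Almost all of the shortfall is the zero count, which has probability 0.99^132 = 26.5%. The chance of a zero count falls to 1.8% at a 3% rate and 0.1% at 5%. Averaged over equally spaced rates, coverage is 88.8% for 1-5% (minimum 73.4%) and 94.2% for 10-30% (minimum 91.4%).

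**Wald coverage in assumed TI subsets (average over the range).**

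| n | Rates 5-10% | Rates 30-50% |
|---|---|---|
| 20 | 77.5% | 92.4% |
| 40 | 88.7% | 93.8% |
| 60 | 89.6% | 94.2% |

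Two single points: 63.9% at n = 20 and rate 5%, and 90.5% at n = 40 and rate 20%.

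**Alternatives.** Clopper-Pearson covered at least 95.0% throughout, and it over-covers in small samples: its average is 98.7% at n = 20 for rates of 5-10%, and 97.1% for 30-50%. Wilson averaged 95.0% to 96.1% over the ranges, with a lowest single value of 91.4% (n = 10, rate 5%).

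**The case against.** The strongest objection is that the operative MDS/CMML plan has not been seen. Protocol 11.0 leaves further analysis detail to the SAP. SAP 1.0 says an MDS/CMML SAP was already approved, and the AML SAP expressly overrides the protocol's outline and uses Clopper-Pearson. The MDS/CMML SAP may do the same. This stands: the gap is shown in the protocol text, not in the analysis that will be run.

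The trigger is also assumed. No rate or subset size comes from the documents, and at moderate rates in the pooled set Wald is close to nominal. This stands too, and it limits the size of the point. It does not justify naming a method that breaks down at zero events, because replacing it after seeing a zero count would be a post hoc choice.

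Clopper-Pearson errs in the other direction by being conservative. That is true, and Wilson largely removes the excess.

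The AML SAP's different choice is not a contradiction, since it concerns another population. Agreed: it shows only that the sponsor already uses an exact interval elsewhere in the same study.

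Finally, no decision depends on these intervals, and a reader can see from the count what 0/n means. That is why the point is minor.

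**Conclusion.** The concern holds as a minor, conditional point about the protocol's wording. Wald is prescribed in three places with no fallback. If a response category is rare (true rates of about 1-5% at n = 132), coverage averages 88.8%. If a TI subset is as small as 20 with rates of 5-10%, it averages 77.5%. Zero events give a zero-width interval. At rates of 10-30% in the pooled set the shortfall is under one percentage point on average.

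The conclusion rests on assumed rates and subset sizes, on all 132 subjects being dosed, and on the MDS/CMML SAP not already naming another interval. The endpoints are secondary and descriptive, with no threshold attached. The AUC equivalence test and the sample size are not affected.

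**What to change.** In the Synopsis (Efficacy) and in Protocol 11.7.1 and 11.7.2, replace Wald with Clopper-Pearson, which matches the AML SAP, or with Wilson if coverage closer to nominal is preferred. First check the approved MDS/CMML SAP. If it already names such an interval, only the protocol wording needs aligning. If it also says Wald, update it too.

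The cost is one word in three places, a possible SAP update, and slightly wider intervals: with Clopper-Pearson, 26/132 widens from 13.6 to 14.2 percentage points and 12/40 from 28.4 to 29.9. Protocol 1.4.3 reports that PK results from 123 treated MDS/CMML subjects have already been presented. The change should therefore carry a dated rationale, and the report should state which interval was prespecified.
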